3. Aesthetic appearance of donor site per surgeon rating (graded 1-10).
4. In patients with tendon exposure, time to complete wound epithelialization (measured as time from surgery to first documentation of complete epithelialization in days).
5. Need for re-operation on forearm or secondary wound care strategy after tendon exposure.
6. Forearm infection requiring surgical drainage and/or antibiotics.

Goal Enrollment:

40 total patients with 1:1 group enrollment. Power analysis was performed to identify necessary sample size to detect an absolute reduction of tendon exposure at four weeks of 15% (25% baseline, 10% expected rate with intervention with power of 80% and alpha 0.05). Under these assumptions, 100 patients would need to be recruited into each arm. Recent historical review of institutional volume demonstrates a rate of approximately 35 forearm flaps annually (2019-2020 data). Assuming a 70% study enrollment rate, we would meet enrollment goals in approximately eight years. This time commitment is felt by the study authors to exceed what is reasonable without first generating preliminary data. The proposed sample size is therefore practically derived based annual surgical volume at this institution and available resources from our industry partner. We recognize the limitations in this study, therefore, and that this design is not truly hypothesis testing. Using the above assumptions, we expect goal enrollment to be met within approximately 18 months.

Covariates Recorded:

1. Demographic data - Age, sex, race, ethnicity, BMI.
3. Medical history - Modified frailty index - 5, diabetes mellitus, coronary artery disease, peripheral artery disease, immunosuppression.
4. Social history - Smoking status (current/former/never, total py), alcohol use pattern
5. Wound surface area in square cm.

Randomization:

Occurs when the patient is scheduled for surgery. A simple randomization strategy will be utilized by creating a randomization list using <https://www.graphpad.com/quickcalcs/randomize1/>, which will ensure equal group distribution. The surgery scheduler will assign patients to their category based on this pre-determined list in consecutive order based on date of surgery scheduling request rather than surgical date to minimize risk of bias.

Consent:

Written informed consent will be obtained at the time of study enrollment and will be stored securely by the Methodist research office. This form is separately attached.

Protocol:

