1. All forearm and ulnar flaps will be harvested using a suprafascial harvest technique.
6. Surgical technique for application of Restrata with split-thickness skin graft.
 1. Restrata will be meshed in a 1:2 fashion to allow for egress of serous fluid and minimize risk of fluid collection.
 2. Restrata will be applied to the entire wound bed not amenable to primary closure and will be underlaid beneath the surrounding skin edges.
 3. A split-thickness skin graft is harvested from patient's thigh at 15:1000 inches and placed on top of the Restrata to cover the entire wound bed. The graft is sutured in place using suture choice of surgeon's preference.
 4. Ultrasound gel is applied to the graft and matrix.
 5. Xeroform gauze bolster is placed over the wound and secured using suture choice of surgeon's preference.
 6. The wrist is wrapped with kerlix gauze and the wrist is immobilized
7. Bolsters are removed at five days, the wound is inspected, and high-definition digital photographs are obtained.
8. The arm remains immobilized for two weeks, and daily xeroform dressing changes are performed by patients, family, or home health per treatment team discretion.
9. Immobilizers are removed at initial follow-up visit at two weeks and high-definition digital photographs are obtained. (Any visit between 12 and 16 days will be considered acceptable as two-week follow-up).
10. If graft incorporation is adequate at two-week follow-up per treating physician discretion, Vaseline® or alternative non-antibiotic ointment will be applied to the graft edges between two and four-week follow-up visits by patients, family, or home health per treatment team discretion. If graft failure occurs by two-week follow-up, Aquacel Ag (ConvaTec Medical Group. Deeside, UK) will be applied to the areas of graft failure as the primary treatment strategy with daily dressing changes.
11. High-definition digital photographs are obtained at four-week follow-up.
12. If graft incorporation is adequate at four-week follow-up per treating physician discretion, no additional wound care will be performed. If graft failure occurs by four-week follow-up, Aquacel Ag will be applied to the areas of graft failure as the primary treatment strategy with daily dressing changes.

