13. If at any point the treating physician feels that the primary treatment strategy is inadequate or inappropriate, a secondary wound care strategy (alternative treatment, negative pressure therapy, surgical debridement, repeat grafting, etc) may be pursued.
14. In any case of incomplete graft incorporation and/or tendon exposure, further photo documentation will be obtained by the patient, family, or home health or wound team, or physician until epithelialization is complete and further wound care is no longer needed. Details of continued follow-up visits and methods of further documentation will be individualized so as to minimize excessive demands on patient resources.
15. Photos of donor sites at each time period will be submitted for evaluation by two independent surgeons who possess expertise in evaluation of free flap donor site wounds and skin grafts but who will not be involved in enrollment of patients in this trial or of management of their wounds. The percentage of graft incorporation and presence or absence of tendon exposure will be documented by each physician in a blinded fashion. The independent surgeons will also rate donor site graft aesthetic appearance on a 1-10 scale in a blinded fashion. Time to

complete epithelialization will be determined by the treating physician, and photo documentation will be submitted for blinded review by the independent surgeons. Any case of failed epithelialization that does not completely epithelialize within 90 days after surgery will be categorized as “greater than 90 days for analysis”, and all study-related patient contact will cease at that time.

16. Descriptive statistics will be reported. Univariate statistics will be used to compare primary and secondary outcomes between groups.

Premature Termination of Study:

This study may be prematurely terminated by the study team at any point if outcomes appear unequivocally worse than standard of care, if unusual types or rates of complications occur, or if any other safety concerns arise. An interim analysis will be performed in order to assess comparative outcomes following successful treatment of 20 subjects and determine whether to proceed with the remainder of the study.

Variables:

1. Surgical harvest technique will not be standardized between surgeons with the exception of requiring suprafascial harvest overlying the area to be grafted.
2. Donor site of split-thickness graft will be at surgeon discretion.

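### Forearm infection (secondary outcome 6) has no time window, and follow-up after week four depends on graft result, so late infections are unequally ascertained between arms

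*Protocol*

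**What the plan says.** In the protocol's outcome lists, both primary outcomes and secondary outcomes 1 and 2 name a time point (four weeks or two weeks). Secondary outcome 6, "Forearm infection requiring surgical drainage and/or antibiotics", names no time point, no window and no method of ascertainment. Secondary outcome 3, appearance, also has no time point.

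Follow-up is set out in the numbered steps of the Protocol section:

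- Step 11, for all patients: "High-definition digital photographs are obtained at four-week follow-up". No later contact is scheduled for everyone.
- Step 12: "If graft incorporation is adequate at four-week follow-up per treating physician discretion, no additional wound care will be performed".
- Step 14: "In any case of incomplete graft incorporation and/or tendon exposure, further photo documentation will be obtained". This continues until the wound has healed, and the visits are not fixed: "Details of continued follow-up visits and methods of further documentation will be individualized".
- Step 15: a wound not healed by 90 days after surgery is classed as such, and study contact then stops.
- Step 15, on the readers: "Photos of donor sites at each time period will be submitted for evaluation by two independent surgeons", and "The independent surgeons will also rate donor site graft aesthetic appearance on a 1-10 scale in a blinded fashion".
- Step 16: primary and secondary outcomes are compared between groups by univariate statistics. No allowance for length of observation is stated.

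**The concern.** Infection is a cumulative outcome, so longer observation can add events and never remove them. Under these steps the length of observation after week four depends on whether the graft took. That is a result arising after randomisation, and the matrix is hypothesised to improve it. If the hypothesis is right, the matrix arm has fewer patients under continued follow-up and so fewer chances to have a late infection recorded. A matrix with no effect on infection could then look mildly protective, and a small increase could be partly hidden.

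Infection is one of the outcomes through which harm from an implanted matrix would show, and the section on premature termination lets the study team stop for unusual rates of complications. The results are also meant as preliminary data, so a systematic tilt could be carried into the planning of a larger trial.

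**Working it through.** The protocol gives no figure for infection, so there is none to reproduce. The 25% and 10% used below come from its Goal Enrollment section. The 100 per arm stated there does follow from them (two-sided alpha 0.05, power 80%, pooled variance, no continuity correction), but it has no bearing on this point.

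**Inputs from the protocol**

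- Common end of scheduled contact: four weeks, taken as day 28.
- Latest end of contact for unhealed patients: day 90.
- Share followed beyond week four: 25% (control) and 10% (matrix). These are the protocol's tendon-exposure rates, used as stand-ins. Patients with incomplete take but no exposed tendon would add to both.
- Arm size: 40 patients at 1:1, so 20 per arm.

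**Inputs assumed**

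- Infection risk by day 28, r: 5%, 10% and 15%.
- The same constant hazard in every patient, healed or not. Any arm difference then comes from follow-up alone.
- Extended follow-up ends at T = 90 (the maximum) or T = 56.
- No infection after day 28 is recorded in healed patients.

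**Observation time.** The maximum ratio is 90/28 = 3.2. Mean observation is 28 + 0.25 × 62 = 43.5 days in controls and 28 + 0.10 × 62 = 34.2 days with the matrix, a ratio of 1.27.

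**Recorded infection.** With h = −ln(1 − r)/28 and R(T) = 1 − exp(−hT), recorded risk in an arm with share p followed on is p × R(T) + (1 − p) × r. The artefact is the difference between arms, (0.25 − 0.10) × (R(T) − r).

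For r = 5% and T = 90: h = 0.00183 and R = 15.2%. Controls: 0.25 × 15.2% + 0.75 × 5% = 7.55%. Matrix: 0.10 × 15.2% + 0.90 × 5% = 6.02%. Difference: 1.53 points.

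| Assumed 28-day risk | R(90) | Control vs matrix, T = 90 | Artefact, T = 90 | Patients per 20 | Artefact, T = 56 |
|---|---|---|---|---|---|
| 5% | 15.2% | 7.6% vs 6.0% | 1.5 points | 0.3 | 0.7 points |
| 10% | 28.7% | 14.7% vs 11.9% | 2.8 points | 0.6 | 1.4 points |
| 15% | 40.7% | 21.4% vs 17.6% | 3.9 points | 0.8 | 1.9 points |

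**Extreme case.** The Background gives a published graft-failure range of 13% to 38%. Setting its two ends as the two arms, with T = 90, gives 2.6 to 6.4 points over the same assumed risks. The largest value is 0.064 × 20 = 1.3 patients.

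**With a common window.** If infection is counted to the same day, with the same ascertainment, in everyone, the artefact is zero by construction.

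**The case against.** The strongest case against has four parts.

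*The end of observation in healed patients is inferred.* Step 12 ends wound care. It does not say that recording of events ends, and the stated stop to study contact at day 90 concerns unhealed wounds. This is fair. The inference rests on the absence of any later scheduled contact, so late infections in healed patients are less likely to be recorded rather than certain to be missed.

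*Step 14 is photo documentation, not infection surveillance.* Photographs may come from the patient or family, while outcome 6 is defined by treatment. This also stands in part, because no ascertainment method is given for either group. Still, continuing contact about an open wound gives more occasion to learn of antibiotics or drainage than no contact.

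*A late infection in an open wound may be a real result of graft failure.* If so, fewer late infections would be part of the matrix's benefit, not bias. That is right, and it limits how much of an observed excess can be called artefact. It is also a reason to prefer a longer common window if records allow one.

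*The time point could be left to an analysis plan.* A plan, not at hand here, could restrict the comparison to four weeks. It could not create later observation in healed patients, because the protocol fixes who is followed.

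A reader might also infer that appearance is biased towards the arm with fewer failures. The documents do not support this. A 1-10 score does not accumulate with time, and blinded ratings at common times exist for all patients up to week four. If last photographs were compared, unhealed patients would be scored later and perhaps after healing, which could favour the arm with more failures. What remains is that the rating to be compared is not named.

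**Conclusion.** The point holds for infection and is minor. An outcome without a window, combined with follow-up that depends on graft result, makes late infections more likely to be recorded in patients whose graft did not take. The tilt favours the arm with fewer such patients.

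In the illustration it is about 1.5 to 3.9 percentage points with follow-up to day 90, and about half that to day 56: less than one patient per arm of 20. This rests on assumed 28-day risks, a constant and equal hazard, tendon exposure standing in for all continued follow-up, and no late recording in healed patients.

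A reader might infer that patients with a failed graft are, as a rule, observed three times as long. The ratio of 3.2 is a maximum, reached only by those still unhealed at day 90. The group followed on is also wider than graft failure, since any incomplete take qualifies. For appearance no direction of bias is claimed. The protocol itself says that the design is not truly hypothesis testing, so an artefact of this size is unlikely to decide anything, but it is easily avoided.

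**What to change.** In Secondary Outcomes, item 6, give infection one window with the same ascertainment in every randomised patient. Either choice works:

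- Surgery to the four-week visit as the compared outcome, with later infections listed separately by arm and labelled as unequally ascertained. Cost: late infections, including any that truly follow from graft failure, leave the comparison.
- Surgery to day 90, taken from institutional records for all patients. Cost: a record check for healed patients.

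In item 3, name the rating of the four-week photograph as the compared value, since later photographs exist only for unhealed patients. The conclusion is then limited to early appearance.

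The change is two lines of text, with no new visits and no change to care.

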Title: Utility of Restrata With Split Thickness Skin Graft to Reconstruct the Forearm Donor Site

NCT Number: NCT04829331

ID: 21-RES-003

Document Date: 22 APRIL 2021

Title:

Utility of Restra (Acera Surgical Inc., St. Louis, MO) in forearm flap reconstruction with donor site healing and function.

Objective:

Understand association between use of Restra (Acera Surgical Inc., St. Louis, MO) in forearm flap reconstruction with donor site healing and function.

Hypothesis:

Use of Restra in combination with split-thickness skin graft for reconstruction of forearm flap reconstruction donor site will be associated with decreased occurrence of tendon exposure at four weeks post-operatively when compared to split-thickness skin graft alone.

Design:

Randomized controlled trial.

Setting:

Single institution, Nebraska Methodist Medical Center

Population:

Adult patients undergoing radial forearm free flap or ulnar forearm free flap at a single institution.

Intervention:

Reconstruction of forearm harvest site using Restra with a split-thickness skin graft.

Control:

Reconstruction of forearm harvest site using split-thickness skin graft alone.

Inclusion Criteria:

1. All patients age 19 or greater that will undergo radial forearm free flap or ulnar free flap.
2. Photo documentation of wound bed at two weeks and four weeks must be obtainable either by physician or patient.

Exclusion Criteria:

1. Active systemic immunosuppression (active use of high-dose steroids ($\geq 40\text{mg}$ prednisone daily or equivalent) or other immunosuppressive medications OR medical conditions causing immunosuppression, i.e. human immunodeficiency virus etc).
2. Diabetes mellitus with most recent Hemoglobin A1c ≥ 10.0 within 30 days prior to surgery.
3. Morbid obesity (BMI >40).
4. Inability to maintain wrist immobilization for full planned period.
5. Severe malnutrition (prealbumin levels <10 mg per dL within 30 days prior to surgery OR BMI <15 (very severely underweight)).
6. Other conditions felt to significantly impair wound healing per surgeon discretion.

Primary Outcomes:

1. Tendon exposure at four weeks post-operatively (Yes/No).

2. Percentage of surface area of split-thickness skin graft incorporation at four weeks post-operatively.

Secondary Outcomes:

1. Tendon exposure at two weeks post-operatively (Yes/No).
2. Percentage of surface area of split-thickness skin graft incorporation at two weeks post-operatively.

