17. Utilization of purse string suture or other methods to narrow the flap donor site wound prior to grafting.
18. Decision to pursue secondary wound care strategy will be at surgeon discretion, including timing and type of treatment.

Funding Source and Funding Needs:

All Restrata products will be provided at no cost to patients by Acera Surgical Inc. No additional financial resources will be necessary to support this project.

Background Information:

Restrata (Acera Surgical, St. Louis, MO) is a synthetic hybrid-scale fiber matrix that possesses a fibrous structure of varying fiber diameters with high porosity [1]. The architecture of the material, which is similar to native extracellular matrix, allows for cell ingress and retention, as well as neovascularization of newly forming tissue, before completely degrading via hydrolysis [1]. The electrospun matrix is composed of two synthetic biocompatible polymers, polyglactin 910 (PLGA 10:90) and polydioxanone (PDO), both of which are used in other (FDA)-cleared devices, including dura substitutes, resorbable sutures, and orthopedic implants [1]. PLGA 10:90 and PDO were specifically selected in order to achieve a matrix with optimal handling properties and a rate of resorption ideally matched to the process of new tissue formation and wound healing. These polymers are co-electrospun into soft, white, compliant, non-woven sheets capable of supporting the natural wound healing process [1]. Once applied to a wound, the matrix supports cellular infiltration, new tissue formation, and wound healing while progressively resorbing into the tissue over the course of two weeks, on average.

Multiple clinical studies, including retrospective analyses, prospective analyses, and case reports have been conducted to evaluate the clinical efficacy of the synthetic hybrid-scale fiber matrix across multiple use cases in the wound care setting. A summary of the clinical studies and

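### The arm is fixed at scheduling and not withheld from the surgeon, so the discretionary exclusion and the wound-narrowing decision can be made with the arm known

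*Protocol*

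**What the plan says.** **Assignment.** Under Randomization, assignment "Occurs when the patient is scheduled for surgery". The mechanism follows: "The surgery scheduler will assign patients to their category based on this pre-determined list in consecutive order based on date of surgery scheduling request". Using the request date instead of the operation date is the stated protection against bias. No section describes concealment of the list, or keeps the arm from the operating surgeon at any stage before grafting.

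**Exclusions that could be settled later.** Item 6 of the Exclusion Criteria reads "Other conditions felt to significantly impair wound healing per surgeon discretion", with no date by which the judgement must be made. Items 2 and 5 are dated to surgery, not to assignment: "Diabetes mellitus with most recent Hemoglobin A1c ≥ 10.0 within 30 days prior to surgery" and "Severe malnutrition (prealbumin levels <10 mg per dL within 30 days prior to surgery". Item 4 is "Inability to maintain wrist immobilization for full planned period". The period concerned follows the operation: "The arm remains immobilized for two weeks" (Protocol, item 8).

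**Wound preparation.** The entry numbered 17 under Variables reads "Utilization of purse string suture or other methods to narrow the flap donor site wound prior to grafting". It has no verb and no rule. Its neighbours cover harvest technique, graft donor site and secondary wound care, all either unstandardized or left to the surgeon.

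**What is protected or recorded.** Two independent surgeons read the photographs blinded (Protocol, item 15). Wound surface area is among the covariates recorded. Whether it is measured before or after narrowing is not stated, and narrowing is not on the list. The comparison described is univariate (Protocol, item 16).

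**The concern.** Randomization makes the arms comparable at the moment of assignment. Decisions taken afterwards by someone who may know the arm can undo that. Here two such decisions bear on the outcome. A surgeon who judges that a patient will heal poorly may exclude that patient more readily in one arm than in the other. A surgeon who knows whether the matrix will be used may narrow the wound more in one arm, without intending to.

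Narrowing matters for both primary outcomes. In the matrix arm the product covers the part of the wound that cannot be closed primarily (Protocol, item 6, second step), so wound preparation determines the area grafted. That area is the base of the graft-incorporation percentage, and it may affect tendon exposure.

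If either decision differs by arm, the arms differ before the product is applied, and blinded reading of the photographs cannot restore the balance. Goal Enrollment presents the trial as preliminary data ahead of a larger commitment. A difference carried over from selection or technique would go into that planning, and more patients would not reduce it.

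**Working it through.** **1. Order of events**

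| Event | Timing in the protocol | Can it follow assignment? | Surgeon judgement? |
|---|---|---|---|
| Assignment | At scheduling | – | No, list order |
| HbA1c and prealbumin exclusions | Within 30 days before surgery | Yes, if the value is obtained after scheduling | Little: numeric thresholds |
| Wrist immobilization | Not dated; concerns two weeks after surgery | Unclear; most naturally means expected inability | Partly |
| Discretionary exclusion | Not dated | Yes | Yes |
| Narrowing before grafting | In theatre | Always | Yes, from its place under Variables |

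The last two rows carry the point. For the laboratory items, knowing the arm does not move a value. Bias would need the ordering of tests to depend on the arm, so this is a weak route.

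**2. Reach of the stated safeguards**

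- Request-date order stops a moved operation date from changing the arm. It does not govern who knows the arm or what is decided afterwards.
- Blinded reading protects assessment, which comes after both decisions.
- Recorded wound area would reveal an imbalance in narrowing only if it is known whether it was measured before or after narrowing.

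**3. The plan's own figure**

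Inputs from Goal Enrollment: 25% versus 10%, power 80%, alpha 0.05 (taken as two-sided), pooled variance, no continuity correction.

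n per arm = [1.960·√(2·0.175·0.825) + 0.842·√(0.25·0.75 + 0.10·0.90)]² / 0.15² = (1.053 + 0.443)² / 0.0225 = 99.5, rounded up to 100.

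This matches the stated 100 per arm. No figure in the protocol is wrong on this point, and the 15-point target serves as the yardstick below.

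**4. Illustrations on assumed figures**

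The protocol gives no rate of late exclusion and none of narrowing. The following shows scale only.

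*(a) One patient dropped.* Assume no true effect, 5 of 20 exposed in each arm, and one patient with exposure risk r removed from one arm and not replaced. The expected false difference in points is 25 − 100·(5 − r)/19.

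| Assumed r | False difference (points) | Share of 15 points |
|---|---|---|
| 0.25 | 0.0 | 0% |
| 0.50 | 1.3 | 8.8% |
| 0.75 | 2.6 | 17.5% |
| 1.00 | 3.9 | 26.3% |

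The standard error of the difference with 20 per arm at 25% is 100·√(2·0.25·0.75/20) = 13.7 points, so the r = 0.50 case is 1.3/13.7 = 0.10 standard errors.

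*(b) Narrowing.* Assume no true effect of the product, that narrowing multiplies exposure risk by k, and that it is used in share a of one arm and b of the other, with the first arm at 25%. The other arm's risk is 25·[1 − b(1 − k)]/[1 − a(1 − k)].

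| k | a versus b | Other arm | False difference (points) |
|---|---|---|---|
| 0.8 | 40% vs 60% | 23.9% | 1.1 |
| 0.6 | 30% vs 70% | 20.5% | 4.5 |
| 0.4 | 20% vs 80% | 14.8% | 10.2 |

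Nothing in the protocol says which row is realistic, or that narrowing changes exposure risk at all. The width of the range is the reason no size is claimed.

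**The case against.** The strongest reply is that late exclusion is inferred. The criteria are entry criteria, no section says that a patient can be removed after assignment, and eligibility may well be settled before the scheduling request. Narrowing is openly listed as unstandardized practice. The protocol itself says that the design does not truly test a hypothesis, and any plausible effect in case (a) is small beside chance.

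Much of this stands, and it limits the point. A reader might infer any of four stronger things, none of which the protocol supports:

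- *That arm-dependent exclusion or narrowing will occur.* The protocol leaves it possible and does not show it. It does not say that the surgeon is told the arm early, only that nothing withholds it.
- *That the laboratory and wrist exclusions are open doors to selection.* The first rest on numeric thresholds and the second most naturally means expected inability. The clear route among the exclusions is item 6.
- *That consent or enrollment follows assignment.* Their order is not stated, and the point does not depend on it.
- *That a rule for analysing every assigned patient is missing.* That rule may properly sit in a statistical analysis plan, which is not shown.

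The reply does not remove the narrowing decision, which always follows assignment because it is made in theatre. Nor does disclosing that a practice varies stop it from varying by arm. Small size relative to chance is a reason for modest severity. It is not a reason to leave an inexpensive gap open, because the standard error conveys chance error and does not convey this bias.

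**Conclusion.** The point holds as a weakness in the stated timing of assignment. The arm is fixed at scheduling and not withheld, and two surgeon judgements, the discretionary exclusion and wound narrowing, can be made with it known. The laboratory exclusions are a weaker third route. The stated safeguards cover none of these.

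The size cannot be estimated from the protocol. The illustrative 0 to 3.9 points for one dropped patient and 1.1 to 10.2 points for unequal narrowing rest wholly on assumed risks and frequencies. The upper ends need extreme assumptions.

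Two readings of the text are involved: that narrowing is left to the surgeon, taken from its place under Variables, and that silence about concealment means that none is planned. If eligibility is in practice completed before the scheduling request, only the narrowing part remains. This is a cheap improvement that should be made. It does not invalidate the trial.

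**What to change.** Amend the Randomization paragraph as follows:

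1. Confirm and record consent and every eligibility item, including the discretionary exclusion and the laboratory values, before assignment.
2. Have the research office, which already stores the consent forms, hold the list concealed in place of the surgery scheduler.
3. Where workable, release the arm in theatre only after the narrowing decision and the wound area have been recorded, for example by sequentially numbered opaque sealed envelope or locked electronic list. Whether and how to narrow stays with the surgeon; only the timing of the record is fixed.

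If theatre release is not workable, the minimum is to lock eligibility before assignment, add narrowing (yes/no) to the recorded covariates, state when wound area is measured relative to narrowing, and report both by arm.

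**Cost.** Theatre release needs product on hand for all 40 cases instead of about 20, unopened until release. The product is supplied free, but Goal Enrollment names the industry partner's resources as a limit on the sample size, so supply must be agreed first. Theatre and research office staff take on small extra tasks. The minimum version needs no extra product. Neither version needs more patients, visits or assessors.

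### The Randomization section calls the method simple yet says it ensures equal groups, and describes no concealment of coming assignments from the scheduler who works through the list

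*Protocol*

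**What the plan says.** Goal Enrollment plans "40 total patients with 1:1 group enrollment". The Randomization section states: "A simple randomization strategy will be utilized by creating a randomization list". It names a web tool for this and says of the result, "which will ensure equal group distribution". It gives no per-arm count for the list, no block size and no stratification.

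On timing and use, randomisation "Occurs when the patient is scheduled for surgery", and the surgery scheduler is to "assign patients to their category based on this pre-determined list in consecutive order based on date of surgery scheduling request". The section gives avoidance of bias as the reason for using the request date and not the operation date. It does not say who holds the list or who can see entries not yet used.

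Three other places bear on the point:

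- Exclusion criterion 6 leaves to the surgeon's judgement whether some other condition impairs healing enough to exclude a patient.
- The Consent section has consent taken at enrolment and the forms kept by the research office. It does not say whether this precedes randomisation.
- Premature Termination of Study says: "An interim analysis will be performed in order to assess comparative outcomes following successful treatment of 20 subjects". It makes no statement about arm sizes at that look.

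**The concern.** Simple randomisation, in its standard sense, assigns each patient independently of the others. Group sizes are then random, and no property of the list ensures that they are equal. A list built to hold equal numbers is restricted randomisation. The sentence claims both, so a reader cannot tell which design was run, and a publication that copies it will misreport the method under either reading.

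The second issue is foreknowledge. A scheduler who works down a pre-determined list may know the next assignment before the patient is entered. Surgeons cannot be blinded at operation, because the matrix is either placed under the graft or not, so they can also keep count of past assignments. Together with a discretionary exclusion and an unstated order of consent and randomisation, this leaves a route by which knowledge of the coming arm could influence who enters. Selection bias of that kind cannot be removed once patients are allocated.

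**Working it through.** **Plan's own figure.** The Protocol gives "25% baseline, 10% expected rate with intervention with power of 80% and alpha 0.05" and concludes "100 patients would need to be recruited into each arm". With a two-sided test, pooled variance and no continuity correction, the mean rate is 0.175 and

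n = [1.960·√(2·0.175·0.825) + 0.842·√(0.25·0.75 + 0.10·0.90)]² / 0.15² = (1.053 + 0.443)² / 0.0225 ≈ 99.5, rounded up to 100 per arm.

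The figure reproduces and is not in dispute. The trial itself has 40 patients.

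**Reading A: truly simple randomisation of 40.** The number in one arm is Binomial(40, 0.5).

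- P(exactly 20/20) = C(40,20)/2⁴⁰ = 12.5%.
- P(24/16 or worse) = 2·P(X ≤ 16) = 26.8%.
- P(25/15 or worse) = 2·P(X ≤ 15) = 15.4%.

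Efficiency relative to 20/20 is 4·n₁·n₂/N². At 24/16 it is 4·24·16/1600 = 0.96. At 25/15 it is 4·25·15/1600 = 0.9375, a loss of about 6%. At 26/14 it is 0.91. Equality is therefore unlikely, but the usual imbalances are cheap.

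**Reading B: a list fixed at 20 per arm, unblocked.** The split among the 40 assigned is 20/20 by construction, and only the label is wrong. Some predictability follows for anyone who tracks the counts:

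- Expected number of final assignments that are fully determined = 2·20/21 = 1.9.
- Expected correct guesses when always guessing the arm that is behind = 20 + 2³⁹/C(40,20) − 0.5 = 23.5 of 40, against 20 by chance.

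A person who can see the list itself knows every coming assignment under either reading.

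**The first 20 assigned.** A split of 12/8 or worse has probability 50.3% under reading A (Binomial(20, 0.5)) and 34.3% under reading B (hypergeometric, 20 drawn from 20 + 20). Neither reading controls balance there. However, the interim look counts treated subjects, while the list runs by scheduling request, so these figures only approximate the split at the look.

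**Permuted blocks as an alternative.** With block sizes 4 and 6 chosen at random and the list cut at 40, simulation of the same guessing strategy gives about 27.6 of 40 correct. That is 7.6 above chance, against 3.5 for the fixed list. Exact 20/20 then occurs in about 77% of lists. Blocks tighten balance along the way, but counts return to equality at each block end, which helps a guesser even when block sizes are undisclosed.

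**The case against.** The strongest reply is that the section does not describe coin-tossing. It describes a list made in advance for 40 patients at 1:1, with equality stated as a property. The natural reading is a list fixed at 20 per arm, with *simple* used loosely for unblocked and unstratified. This largely stands. A reader might infer that the 1:1 split will not be delivered, but the documents do not show how the tool builds the list, and under the fixed-list reading the split is delivered among those assigned. The 12.5% and 26.8% figures apply only if the word *simple* is taken literally.

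A reader might also infer that balance at the 20-subject look has been promised and broken. It has not: no section promises it. Cancellations, reordered operation dates and unsuccessful treatments could unbalance that look under any scheme.

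On concealment, the Protocol does not say that the list is open, and the order of assignment is fixed by request date expressly to limit bias. The independent surgeons who read the photographs for the primary outcomes are blinded and not involved in enrolment (Protocol, step 15). That protects outcome assessment, but it does not protect against selective entry. What remains is that no concealment is described, not that foreknowledge has been shown.

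Finally, the Protocol itself says that its sample size is set by practical limits and that the design is not a true hypothesis test. This lowers the weight of any loss of precision. It does not excuse a method statement that contradicts itself.

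**Conclusion.** The point holds as an internal contradiction in the description of the method, together with an undescribed concealment step. The numerical consequence is small: at most a few per cent of efficiency under the literal reading (about 6% at 25/15), and none among the 40 assigned under a fixed 20/20 list. The stronger reasons to act are accurate reporting and protection against selection bias, and the size of that bias cannot be derived from the documents.

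The conclusion rests on the standard meaning of simple randomisation, on the surgeon's inevitable knowledge of the arm at operation, and on the absence from the Protocol of any statement about who sees the list. If a separate randomisation procedure already provides concealment, only the wording needs to change. It would go too far to conclude that permuted blocks are required: the figures show a trade-off between balance and predictability, not a clear gain.

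**What to change.** Amend the Randomization section in two respects.

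1. Delete *simple* and state the scheme actually used, for example a computer-generated random list restricted to 20 assignments per arm. If assignment really is independent for each patient, delete the claim of equal groups instead.
2. State that the research office, which already stores the consent forms, holds the list and releases one assignment at a time to the scheduler, only after consent and eligibility are confirmed and recorded.

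The cost is an amended sentence or two, a new list if the present one is not of the stated kind, and one extra administrative step each time a patient is scheduled. Concealed release removes the scheduler's view of coming assignments. It does not remove the small predictability at the end of a fixed list (about 1.9 assignments on average).

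Permuted blocks are optional. They would improve balance among those assigned by the time of the interim look, but raise predictability in a single-site trial whose surgeons are not blinded. If they are chosen, the trade-off should be acknowledged and the block sizes made to sum to 40.
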